Immediately after the ambulatory baseline, the participant will be admitted to the Center for Clinical Investigation (CCI) at BWH on Day 1. They will be scheduled to sleep for 10 hours overnight at the CCI (centered at their usual times), and their sleep will be recorded with standard polysomnography (PSG) on some or all of the nights. Upon awakening the next morning (Day 2), the participant will begin the **first Baseline Day**. They will be given isocaloric, nutrient-controlled meals (breakfast, lunch, dinner) and will be scheduled to sleep again for 10 hours overnight. This will continue for the remaining baseline days. Near the end of the first Baseline segment (approximately Day 5), they will have an IV catheter inserted into a forearm vein for blood sampling. After awakening the next morning (~Day 6) after an overnight fast, the participant will undergo an assessment of their resting metabolic rate via indirect calorimetry. This will be followed by a Mixed Meal Response at breakfast to evaluate their baseline glucose and insulin response to a meal (see below for details). Frequent blood samples for melatonin will also be drawn to assess the duration of melatonin secretion and melatonin levels during the metabolic assessments, and this sample collection will continue throughout the next three days (~Days 6-8). Upon awakening on Day 7 after an overnight fast, the participant will undergo an assessment of their resting metabolic rate via indirect calorimetry again, and this will be followed by a baseline insulin-modified IV glucose tolerance test (GTT) that will be carried out to assess insulin sensitivity ( $S_I$ ), acute insulin response (AIRg), and glucose effectiveness (see below). The IVGTT will be scheduled to begin at the same time as the Mixed Meal Response on the previous day. Sample collection for the IVGTT will be completed by approximately 3 hours later (4 hours after wake time). Beginning in the early afternoon, ambient lighting will be lowered to <15 lux and ~hourly blood samples for melatonin endogenous circadian rhythm assessment will be drawn. Sleep will be scheduled at the same time as Nights 1-6, and blood sampling will continue throughout the night. Sample collection for the circadian rhythm of melatonin will be completed by approximately 10 hours after wake time, at which time the sampling IV will be removed and the lighting will be returned to normal.

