The next 7 nights are the **First Sleep Intervention** and will depend on the randomization order. In the Sleep Restriction Group with Extended Duration Artificial Light At Night (ALAN) first, the sleep episodes will be shortened to 5 hours, centered at the same time as the baseline sleep (with bedtime 2.5 hours later and wake time 2.5 hours earlier). In the Sleep Restriction group without Extended Duration ALAN, the sleep episodes will be shortened to 5 hours as in the ALAN Condition (centered at the same time as the baseline sleep with bedtime 2.5 hours later and wake time 2.5 hours earlier), but the participant will remain sitting in bed in near darkness (< 1 lux) for the 2.5 hours before and after the 5-hour sleep episode, such that their exposure to room lighting and activity (14 hours/day) will remain similar to that in the Baseline condition. The timing of meals in both conditions throughout this intervention segment will remain the same as on the Baseline days.

Near the end of the first sleep intervention (~Day 14), each participant will undergo a re-assessment of their resting metabolic rate via indirect calorimetry at the same time as during Baseline. This will be followed by a Standardized Mixed Meal Response at breakfast to re-evaluate their glucose and insulin response to a meal, along with frequent blood samples to assess duration of melatonin secretion and melatonin levels during the metabolic assessments. This sample collection for melatonin will continue throughout the next three days (~Days 14-16). Near the end of the first sleep intervention (~Day 15), an ivGTT re-assessment will be carried out to assess insulin sensitivity ( $S_I$ ), acute insulin response (AIRg), and glucose effectiveness. This will begin at the Detailed Protocol, version 11

same time as the Baseline ivGTT. Sample collection for the ivGTT will be completed by approximately 3 hours later. Beginning in the afternoon, ambient lighting will be lowered to <15 lux and frequent blood samples for re-assessment of melatonin and cortisol circadian rhythms will be drawn, continuing until the following afternoon .

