**Objective alertness assessment.** At approximately hourly intervals throughout the scheduled wake episodes, participants will take a modified Karolinska Drowsiness Test (KDT [107, 120, 121]) to evaluate objective alertness. The KDT is a standardized procedure for providing a highly sensitive, objective EOG (incidence of slow eye movements and eye blink rates) and EEG measures to assess alertness. During the KDT, participants are asked to remain still while fixing their gaze for ~4 minutes, avoiding frequent eye blinks, eye movements and body movements. This test allows for reliable collection of EEGs of high signal quality. These objective measures of sleepiness have been shown to vary with circadian phase and duration of wakefulness[122-126]. Our staff and the technical staff of the CCI routinely conduct such recordings. EEG will also be recorded throughout the wake episodes to document wakefulness [107].

**Subjective alertness assessment.** Throughout the study, participants will complete computer-administered alertness assessments at approximately hourly intervals when they are awake. These will include the Karolinska Sleepiness Scale (KSS) and a Visual Analog Scale (VAS). The KSS requires the participant to select a number on a scale from 1 to 9 spanning the range from very sleepy to very alert. The task takes less than 1 minute, and KSS scores have been shown to oscillate with the core body temperature and plasma melatonin rhythms [109-111]. Visual Analogue Scales (VAS) consist of a horizontal line drawn on the computer display with each end of the line labeled with the extremes of a subjective continuum, e.g. sleepy-alert. Participants indicate a position on the line that best describes how they feel at that moment. The task takes less than 1 minute to complete, and subjective estimates have been shown to vary with circadian phase and sleep loss [112-115].

**Neurobehavioral performance assessment.** Throughout the study, participants may be asked to complete additional computer-administrated performance test batteries several times per wake period. This battery may include the following tests:

- **Psychomotor Vigilance Task** (PVT) to assess **sustained attention performance**. The PVT is a test of visual reaction time (RT) in which the subject is asked to maintain the fastest possible RTs to a simple visual stimulus for ~10 minutes. The inter-stimulus interval varies randomly between 2-10 seconds.

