- Tests of emotional memory and/or perception, such as the Emotional Memory Task in which subjects view images, slides, or scenes ranging in emotionality from standardized and validated stimuli sets (e.g. International Affective Picture System; IAPS or Nencki Affective Picture System; NAPS) and are asked to rate and/or remember the scenes for later testing; the Emotional Trade-off Task, in which subjects view images consisting of an object, either emotional (i.e. a car wreck) or neutral (i.e. a taxi), composited onto a background (i.e., a city street) and are later shown objects and backgrounds in isolation and asked to remember whether or not they saw an identical or similar item; and the Morphed Faces Task, where subjects view a series of pictures created by separately morphing a neutral face with 3 different emotional faces (Angry, Happy and Sad) and are asked to identify each face's emotional category, as well as rate their interpretation of its intensity and valence (negative to positive).

Voice recording collection. During scheduled wake episodes a speech task may be administered in addition to each scheduled neurobehavioral test battery proposed above. The speech task will be administered via computer and will take less than 2 minutes in total. Each speech task begins with a prompt to the participant that their voice will be recorded throughout the task, and to make sure they are sitting facing the computer monitor and microphone. They are then asked to read a list of 10 sentences from the Harvard Sentences corpus [IEEE Recommended Practice for Speech Quality Measurements. IEEE Trans Audio Electroacoust. 1969;17(3):225-246. doi:10.1109/TAU.1969.1162058].

Steps for a single speech task:

1. The computer program first generates a random 3-digit number and picks a list (10 sentences) from the Harvard Sentences for the current assessment.
2. One sentence at a time is presented to the subject on the computer monitor. After reading out the sentence, the subject presses the spacebar on the keyboard to proceed to the next sentence.
3. After recording the 10 sentences by repeating Step 2, the 10 recordings are saved separately as waveform audio files (WAV) under a folder named by the random 3-digit number from Step 1.

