**Analysis of voice recording (Exploratory Aim 8).** Human vocal parameters will be collected during specified wake times. Power spectral density, intensity, pauses, reading mistakes, and automatic speech recognition (ASR) system errors are extracted from each audio file containing one sentence recording. These features will be aggregated at various scales (over each list or subject). Different acoustic analysis techniques and computer programs will be used to extract these features in a retrospective manner. The table below lists our proposed features.

Feature	Note
Duration (seconds) and percentage of voiced segments	
Duration (seconds) and percentage of vocalic segments	
Number, duration (seconds), and location of pauses	Natural and unnatural pauses
Reading mistakes (counts)	Stumbling, paralexia, deletion, and addition
ASR errors (counts)	
Power spectral density (square of amplitude)	Mean, variance, min, max, and slope
Intensity analysis (decibel)	Mean, variance, min, max, and slope
Jitter (seconds), shimmer (seconds), and HNR (%)	Provided by the Praat Software

After preprocessing and extraction, vocal features will be decorrelated with confounding factors, including age, sex, BMI, and other demographic information of subjects. Any feature correlated to confounding factors will be replaced by the residue of a multivariate linear regression approximating the value of the feature from confounding factors. One-way ANOVA will be performed to examine if vocal features are significantly different between recordings from different sleep-wake conditions (baseline, restricted sleep with extended duration ALAN, and restricted sleep without extended duration ALAN). Mann-Whitney U tests will be performed to compare between conditions. For repeated vocal parameter measurements during the same experimental segment, they will be aggregated and averaged over the segment duration to achieve global-level comparison.

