For Specific Aim 3, we estimate that we will have 84% power ( $\alpha=0.0167$ , 2-sided paired t-test) with 20 subjects to detect a difference as small as 40 minutes (0.66 hrs) in the duration of melatonin secretion (1 hr with ALAN vs. 20 minutes without ALAN, assuming common SD=48 minutes). This should be more than adequate to detect the expected difference in melatonin secretion, given that we previously showed that evening exposure to room light shortened the duration of melatonin secretion by about 90 minutes (compared to dim lighting), even when participants remained in darkness for 8hrs/night during sleep[94]. Because participants in the current proposed

study will be exposed to room light for an extra 5 hrs/day in the sleep restriction with ALAN condition, we expect to see a more than 3-hour difference in the duration of melatonin secretion with and without ALAN.

For Exploratory Aim 4, we will consider two primary outcomes. We estimate that we have 85% power ( $\alpha=0.025$ , 2-sided paired-sample t-test) to detect an 20% difference in the change (25% with ALAN, SD=28% vs. 5% without ALAN, SD=6%) in levels of long-chain, highly unsaturated triglycerides, which have been associated with insulin sensitivity. Moreover, we estimate we will have 85% power to detect a difference as little as 11% in the change (5% with ALAN, SD=6% vs. 18% without ALAN, SD=19%) in levels of short-chain, highly saturated triglycerides, levels of which have been associated with increased diabetes risk.

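### The voice analysis averages every recording in a segment, so any session held in the extra wake hours of sleep restriction mixes a time-of-day difference into the restriction effect

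*Combined protocol and SAP*

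**What the plan says.** Aim 8 (II. Specific Aims) hypothesises that a week of sleep restriction changes objective vocal parameters, both with and without ALAN.

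- **Collection** (V. Study Procedures, Voice recording collection): "During scheduled wake episodes a speech task may be administered in addition to each scheduled neurobehavioral test battery proposed above". The paragraph on neurobehavioral performance assessment says that batteries may be given several times per wake period. The analysis section refers to specified wake times, but no section lists them.
- **Analysis** (VI. Biostatistical analysis, Analysis of voice recording): features that correlate with age, sex, BMI or other demographic factors are replaced by regression residuals. Baseline, restriction with ALAN and restriction without ALAN are then compared by one-way ANOVA and Mann-Whitney U tests. Repeated measurements within a segment are handled thus: "they will be aggregated and averaged over the segment duration to achieve global-level comparison".
- **Schedule** (V. Study Procedures): on baseline days participants "will be scheduled to sleep again for 10 hours overnight". Under restriction with ALAN "the sleep episodes will be shortened to 5 hours, centered at the same time as the baseline sleep", so that 2.5 h of wake are added at each end of the night. The condition without ALAN has the same 5-h sleep episode, but the 2.5 h on each side are spent sitting in bed in near darkness.

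**The concern.** The three segment means do not necessarily cover the same hours of the day. A baseline mean can contain only recordings from the 14-h waking window. A restriction mean can also contain recordings from hours when the participant was asleep at baseline. If a vocal feature varies with time of day, the restriction mean then shifts even when restriction has done nothing to the voice at any given hour.

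The planned adjustment cannot remove this. Age, sex, BMI and other demographic factors are constant within a person, whereas the shift arises within the person, between hours. Clock time, circadian phase and hours awake do not enter the voice analysis.

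A time-of-day effect is not far-fetched on the protocol's own account. Of its EEG and EOG alertness measures it says: "These objective measures of sleepiness have been shown to vary with circadian phase and duration of wakefulness". That statement is not about voice, but a vocal feature that tracks sleepiness could plausibly behave in the same way. At stake is whether a difference found under Aim 8 can be attributed to sleep restriction.

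**Working it through.** **1. Hours awake.** Inputs are the 10-h baseline and 5-h restricted sleep episodes in V. Study Procedures.

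- Baseline wake: 24 − 10 = 14 h.
- Restriction wake: 24 − 5 = 19 h.
- Added wake: 19 − 14 = 5 h, which equals 2 × 2.5 h.

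This reproduces the document's own figure. The section on sample size and power states that participants in the "study will be exposed to room light for an extra 5 hrs/day in the sleep restriction with ALAN condition". Because the short sleep episode is centred on the long one, all 5 h lie inside the baseline sleep episode, and no baseline recording can exist at those hours.

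**2. What the segment mean estimates.** Let s be the share of a condition's sessions held in the added hours. Let D be the difference in the feature between the added hours and the common hours for a person whose voice is unaffected by restriction. Let e be the restriction effect at a given hour, taken as constant for simplicity.

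- Baseline mean = common-hour level.
- Restriction mean = common-hour level + e + s × D.
- Restriction minus baseline = e + s × D.

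The bias is s × D. It is zero if no session falls in the added hours or if the feature does not vary with time of day.

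**3. The share s.** Session times are not given, so s must be assumed.

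| Assumed layout | s |
|---|---|
| No session in the added hours | 0 |
| 1 of 6 sessions | 1/6 = 17% |
| 1 of 5 sessions | 1/5 = 20% |
| 2 of 8 sessions | 2/8 = 25% |
| Evenly spaced over wake | 5/19 = 26.3% |
| 2 of 6 sessions | 2/6 = 33% |

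**4. The bias for assumed values of D.** The documents give no D for voice. With even spacing:

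- D = 0.5 SD: 0.263 × 0.5 = 0.13 SD.
- D = 1.0 SD: 0.263 × 1.0 = 0.26 SD.
- D = 1.5 SD: 0.263 × 1.5 = 0.39 SD.

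**5. ALAN versus no ALAN.** Taking D as the same in both conditions, the bias in this contrast is (s with ALAN − s without ALAN) × D. It cancels if the shares are equal. If only the ALAN condition has added-hour sessions and these are evenly spaced, it is again 0.263 × D.

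**6. After the fix.** Using only recordings from the common 14-h window sets s to 0 in every condition, so this source of bias disappears.

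**The case against.** The strongest reply is that nothing places a voice session in the added hours. The task is optional, the batteries are optional, and their times are not given. If every session falls within the usual waking hours, the bias is nil. This stands: a reader might infer that a quarter of restriction recordings are certainly affected, but 26% is one assumed layout. It does not dispose of the point, because the procedures permit sessions throughout scheduled wake and the averaging rule contains no safeguard.

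Second, the two restriction conditions should not be treated alike. Without ALAN the added hours are spent confined to bed in near darkness, where VII. Risks and Discomforts says reading will be difficult. The task requires reading from a monitor, with the microphone set up at a desk. Sessions at those hours are therefore less likely. This stands, and it narrows the problem for baseline versus no ALAN while opening it for ALAN versus no ALAN.

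Third, being awake at those hours is part of sleep restriction, so an all-wake average could be defended as a total effect. That is a fair reason to keep and report the added-hour recordings. It does not justify comparing them with baseline recordings from other hours under a single mean.

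Fourth, a reader might infer a particular inflated false-positive rate. The documents do not support one. They give no night-day difference or variance for voice. The planned Mann-Whitney test, applied to segment means, also ignores the pairing and is conservative when a person's means are positively correlated. Rejection rates computed for a paired test would not describe this plan. A conservative test still leaves the estimated difference biased.

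**Conclusion.** The concern holds as a weakness of the stated averaging rule, conditional on sessions being held in the added hours. The rule cannot separate a change in the voice from a change in the hours sampled, and the demographic adjustment does not help. The bias is s × D, with s between 0 and 33% over the layouts considered (26% if evenly spaced) and D unknown. It is clearest for baseline versus restriction with ALAN. It is less likely for baseline versus restriction without ALAN, and in that case it may carry over to the comparison of the two restriction conditions.

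Calling the added hours biological night would also go further than the documents allow. Habitual sleep is 7 to 9 h, so a centred 10-h episode extends (10 − 9)/2 = 0.5 h to (10 − 7)/2 = 1.5 h beyond it on each side. The firm statement is only that baseline never samples these hours.

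Aim 8 is exploratory and has no power statement. The three primary outcomes are unaffected. This is a cheap improvement.

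**What to change.** In the voice paragraph of VI. Biostatistical analysis:

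- Base all three between-condition comparisons on recordings within the 14-h window that is scheduled wake in every condition. Match sessions by time relative to the participant's habitual wake time, not the earlier wake time of restriction days.
- Alternatively, fit a mixed model with participant as a random effect and condition and time-of-day bin as fixed effects, using only the bins common to all conditions.
- Report added-hour recordings separately and descriptively. Compare the two restriction conditions at those hours only if both have such sessions.
- List the planned session times, so that the common window can be applied without judgement after the data are seen.

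The cost is a few sentences and no new data. With even spacing, about a quarter of the restriction recordings (5/19) leave the baseline comparison, with a small loss of precision in the segment means. If no session falls in the added hours, nothing is lost.

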### Sample size and power calculation

We will consider three primary outcomes: insulin sensitivity for Specific Aim 1; glucose AUC for Specific Aim 2; and duration of melatonin secretion for Specific Aim 3. Sample size and power calculations are based on results from our previous studies. In the study of one week of sleep restriction to 5 h/night[13], we observed a ~28% decrease in insulin sensitivity as assessed by ivGTT. We anticipate a similar effect on insulin sensitivity in participants assigned to the Sleep Restriction with extended duration Artificial Light At Night (ALAN) group in the proposed study, given the identical conditions of 1 week of sleep restriction. In a separate study, no impairment of glucose tolerance was observed in a group of participants exposed to sleep restriction without extended duration exposure to ALAN (See Preliminary Studies, Fig. 3). With 20 subjects, we have 83% power ( $\alpha=0.05/3=0.0167$ , 2-sided paired t-test) to detect as little as a 13% difference between the conditions in the change from baseline (18% change with ALAN vs. 5% change without ALAN) in insulin sensitivity (assuming the common standard deviation (SD) of the change is 16%). This should be more than adequate to detect the difference in insulin sensitivity we expect to observe in the proposed study. For Specific Aim 2, with 20 subjects, we estimate that we have 83% power ( $\alpha=0.0167$ , 2-sided paired t-test) to detect as little as a 3.65% difference between the conditions in the change of glucose AUC (assuming common SD= 4.5%). This should be more than adequate to detect the difference in glucose AUC we expect to observe, given that we have previously observed an over 20% change in glucose AUC following a prior history of recurrent circadian disruption combined with chronic sleep restriction[32].

For Specific Aim 3, we estimate that we will have 84% power ( $\alpha=0.0167$ , 2-sided paired t-test) with 20 subjects to detect a difference as small as 40 minutes (0.66 hrs) in the duration of melatonin secretion (1 hr with ALAN vs. 20 minutes without ALAN, assuming common SD=48 minutes). This should be more than adequate to detect the expected difference in melatonin secretion, given that we previously showed that evening exposure to room light shortened the duration of melatonin secretion by about 90 minutes (compared to dim lighting), even when participants remained in darkness for 8hrs/night during sleep[94]. Because participants in the current proposed

study will be exposed to room light for an extra 5 hrs/day in the sleep restriction with ALAN condition, we expect to see a more than 3-hour difference in the duration of melatonin secretion with and without ALAN.

For Exploratory Aim 4, we will consider two primary outcomes. We estimate that we have 85% power ( $\alpha=0.025$ , 2-sided paired-sample t-test) to detect an 20% difference in the change (25% with ALAN, SD=28% vs. 5% without ALAN, SD=6%) in levels of long-chain, highly unsaturated triglycerides, which have been associated with insulin sensitivity. Moreover, we estimate we will have 85% power to detect a difference as little as 11% in the change (5% with ALAN, SD=6% vs. 18% without ALAN, SD=19%) in levels of short-chain, highly saturated triglycerides, levels of which have been associated with increased diabetes risk.

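### The three primary outcomes are powered at a fixed Bonferroni 0.0167 and Section VI states no testing rule; naming Holm's step-down would keep the 5% family error and add power near the minimum detectable effects

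*Combined protocol and SAP*

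**What the plan says.** Section VI, under Sample size and power calculation, opens with "We will consider three primary outcomes: insulin sensitivity for Specific Aim 1; glucose AUC for Specific Aim 2" and names duration of melatonin secretion as the third primary outcome, for Specific Aim 3. Each is powered separately at 0.05/3 = 0.0167, two-sided, by paired t-test:

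- Insulin sensitivity: "With 20 subjects, we have 83% power" for "a 13% difference between the conditions in the change from baseline", "assuming the common standard deviation (SD) of the change is 16" per cent.
- Glucose AUC: 83% power for "a 3.65% difference between the conditions in the change of glucose AUC (assuming common SD= 4.5" per cent).
- Melatonin: 84% power "to detect a difference as small as 40 minutes (0.66 hrs) in the duration of melatonin secretion", with an SD of 48 minutes.

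The same section expects larger effects than these: a fall in insulin sensitivity similar to the roughly 28% seen earlier, and a melatonin difference of more than 3 hours. It also cites a change of over 20% in glucose AUC from a previous study.

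The analysis paragraph at the start of Section VI lists paired t-tests or Wilcoxon tests, linear mixed models, and both intent-to-treat and per-protocol analyses. It rules out an interim analysis. It gives no multiplicity rule, and it calls only insulin sensitivity and glucose tolerance primary, with melatonin duration entering the mediation analysis. The 0.025 level for Exploratory Aim 4 covers two other outcomes and lies outside this family.

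**The concern.** If the 0.0167 of the power section is carried into the analysis, each primary outcome is judged at that level whatever the other two show. Holm's procedure tests the smallest of three p-values against 0.05/3, the next against 0.05/2 and the last against 0.05, stopping at the first failure. Its first step is the Bonferroni test, so nothing is lost in the decisions. Once one hypothesis is rejected, the remaining ones face a less strict threshold.

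This trial is a natural case for it. The plan expects melatonin duration to differ by more than four times its detectable difference (180/40 = 4.5), so that test should be rejected first. At stake is power for the two metabolic outcomes in a 33-day inpatient study that will have only 20 completers. The analysis text is silent, so a rule has to be written in any case.

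**Working it through.** **Inputs.** All effects, SDs, the sample size and alpha come from Sample size and power calculation. The correlation between outcomes is not in the documents; I assumed 0, 0.5 and 0.8.

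**Step 1: reproduce the stated power.** Paired t-test, n = 20, df = 19, d = difference/SD, noncentrality d × √20, two-sided 0.0167, with the stated SD read as the SD of the paired difference.

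| Outcome | d | Computed | Stated |
|---|---|---|---|
| Insulin sensitivity | 13/16 = 0.8125 | 83.2% | 83% |
| Glucose AUC | 3.65/4.5 = 0.811 | 83.0% | 83% |
| Melatonin duration | 40/48 = 0.833 | 85.2% | 84% |

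With 0.66 h over 0.8 h the melatonin figure is 84.4%. The plan's figures are reproduced.

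**Step 2: power at Holm's later thresholds.** For insulin sensitivity, exact power is 87.4% at 0.025 and 93.1% at 0.05. For glucose AUC it is 87.3% and 93.0%.

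**Step 3: hand check with melatonin certain to be rejected and outcomes independent.** Insulin sensitivity is then rejected if its p ≤ 0.025, or if its p lies between 0.025 and 0.05 and glucose AUC has p ≤ 0.025.

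- Glucose AUC real at 3.65%: 0.8742 + (0.9312 − 0.8742) × 0.8730 = 0.924.
- Glucose AUC null: 0.8742 + (0.9312 − 0.8742) × 0.025 = 0.876.
- False rejection of a null glucose AUC, with insulin sensitivity real: 0.025 + 0.025 × 0.8742 = 0.047, against 0.0167 under Bonferroni.

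**Step 4: simulation.** 400,000 trials per scenario, three paired t-tests, n = 20. Power is in per cent, in the order insulin sensitivity / glucose AUC / melatonin. Minimum means the planned detectable effect. Correlation is 0 unless given.

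| Scenario | Bonferroni | Holm | All three, Bonferroni to Holm |
|---|---|---|---|
| All at minimum | 83 / 83 / 85 | 91.8 / 91.8 / 92.9 | 58.9 to 80.9 |
| Same, correlation 0.5 | 83 / 83 / 85 | 90.3 / 90.3 / 91.5 | 66.5 to 83.4 |
| Same, correlation 0.8 | 83 / 83 / 85 | 88.9 / 88.9 / 89.8 | 73.1 to 85.9 |
| Melatonin 3 h, others at minimum | 83 / 83 / 100 | 92.4 / 92.3 / 100 | 69.1 to 86.4 |
| Melatonin 3 h, insulin sensitivity at minimum, AUC null | 83 / 1.7 / 100 | 87.6 / 4.7 / 100 | – |
| Insulin sensitivity and melatonin at minimum, AUC null | 83 / 1.7 / 85 | 87.0 / 4.4 / 88.7 | – |
| Only insulin sensitivity real | 83.2 / 1.7 / 1.7 | 83.3 / 2.4 / 2.4 | – |
| Larger effects: d = 23/16, 20/4.5, 180/48 | 99.98 / 100 / 100 | 100 / 100 / 100 | 99.98 to 100 |

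Independent check of the first row: 0.8316 × 0.8302 × 0.8522 = 0.588.

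The chance of at least one rejection is the same under both methods (99.6% in the first row), because the first step is identical.

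**Step 5: family-wise error under Holm.** It is 4.97% with all three null, 4.7% with only insulin sensitivity real, 4.4% with insulin sensitivity and melatonin real, and 4.9% with only a 3-hour melatonin effect.

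**Step 6: sensitivity to the SD.** If the common SD belongs to each condition's change, the SD of the difference is SD × √(2(1 − r)). It equals the stated SD only at r = 0.5. At r = 0, each d is divided by √2. Bonferroni power is then about 49 / 49 / 52%, Holm gives about 58 / 58 / 61%, and power for all three goes from 12% to 30%.

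**The case against.** The strongest reply is that nothing is broken. Bonferroni is valid, its power figures are right, and the 13% and 3.65% are minimum detectable differences rather than expected ones. With 28% against 5% for insulin sensitivity, Bonferroni power is 99.98%, so there is almost nothing to gain. That stands, and it limits the point to effects near the planned minimum. It does not dispose of it: the plan sizes the trial on those smaller effects. The over-20% glucose AUC figure also comes from circadian disruption combined with chronic sleep restriction, not from the contrast tested here.

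A reader might infer that a sure melatonin rejection by itself lifts the metabolic outcomes to 92%. It does not. It moves the next threshold to 0.025, worth about four points (83.2% to 87.4%). The remainder needs the other metabolic outcome to be significant too.

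A reader might also infer that Holm costs nothing. It costs no participants and no family error, but a true null outcome is rejected more often when the other two are real (about 1.7% to 4.4–4.7%). Simple simultaneous confidence intervals stay at the 0.0167 level and may not match the Holm decisions.

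Finally, it is tempting to say that the plan commits itself to Bonferroni for the final tests. The documents support less: 0.0167 appears only in the power section, and the analysis text prescribes nothing.

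**Conclusion.** The point holds as an efficiency improvement together with a gap in the stated testing rule, not as an error in the plan. For insulin sensitivity the gain is about 6 to 9 points if all three effects are real at the planned minimum, about 4 if one other outcome is real, and about 0.1 if none is. It is about nil if the larger expected effects occur. The clearest benefit is in the probability of showing all three: 59% to 81% at correlation 0 and 73% to 86% at 0.8.

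These figures rest on 20 completers, paired t-tests, the stated SDs read as SDs of the paired difference, and assumed correlations between outcomes. The control of family-wise error rests on none of these beyond valid individual p-values.

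**What to change.** In Section VI, before outcome data are analysed:

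1. State that insulin sensitivity, glucose AUC and melatonin duration form one family tested by Holm: smallest p-value against 0.0167, next against 0.025, last against 0.05, stopping at the first failure.
2. Designate one primary-analysis p-value per outcome, choosing among paired t-test, Wilcoxon and mixed model and between intent-to-treat and per-protocol. Holm's ordering is not defined without this.
3. Reconcile the opening analysis paragraph, which names two primary outcomes, with the power section, which names three.
4. Keep the 0.0167 power figures and label them conservative lower bounds.
5. Say that simultaneous confidence intervals are given at the 0.0167 level and may not match the Holm decisions.

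The Holm rule is one sentence; items 2 and 3 take a short paragraph. No participants, visits or assays are added.
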